## **2.4.9 Analyses of pharmacokinetic and pharmacodynamic variables**

### **2.4.9.1 Pharmacodynamic analysis**

Pharmacodynamic endpoints include sphingomyelin and its metabolites, including sphingomyelin accumulation in liver tissue, along with ceramide in DBS. These endpoints will be analyzed using pharmacodynamics population. Observed and change from baseline values will be summarized at scheduled visits. Summary plots over time for pre-infusion values will be provided.

### **2.4.9.2 Pharmacokinetic analysis**

Plasma concentration-time data will be analyzed by non-compartmental methods, or nonlinear mixed effects modeling, based upon patient age and data suitability. Values will be reported for individual patient and summarized by age group cohorts, dose level, manufacturing process and study week as appropriate.

For ease of presentation, mean values will be arithmetic mean unless specified. Concentration values below the plasma assay limit will be treated as zero in calculating mean values. Mean values below Lower Limit of Quantification (LLOQ) will be reported as LLOQ in the tables and not plotted in the figures if after  $C_{max}$ . Mean calculations and their associated statistics will be generated from unrounded numbers and may differ slightly from those values that would be determined using the rounded numbers displayed in the tables. Values expressed in all tables will be for ease of presentation and will not be meant to imply accuracy to more than 3 significant figures.

Pharmacokinetic parameters of olipudase alfa may be summarized using descriptive statistics such as arithmetic mean, geometric mean, SD, standard error of the mean (SEM), coefficient of variation (CV [%]), minimum, median, maximum, and number of observations for each study visit, dose level and age group cohort under the responsibility of Pharmacokinetics, Dynamics and Metabolism (PKDM) using Phoenix WinNonlin Professional, Version 8.1, or NONMEM (VII or above) running on a Linux cluster.

Associations between ADA variables (eg, ADA status) and PK of olipudase alfa (eg, AUC) will be explored for olipudase alfa at selected PK visits. If applicable, plot of olipudase alfa PK (eg, AUC) versus the selected PK visit may be provided by ADA classifications for the olipudase alfa treatment group. Nab data may be explored as appropriate.

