9.3.8 Pharmacokinetics

For both adult and pediatric patients, PK testing will only occur yearly for the first 5 years and upon the introduction of Process C(█) or Process C(█) at any time during the study. For Process C(█), if treatment is not interrupted, PK sample collection will take place at the patient's last infusion under the current manufacturing scale and at the first infusion Process C(█). For introduction of drug product from Process C(█), if treatment is not interrupted, PK sample collection will take place at the second infusion under Process C(█). In case reintroduction of olipudase alfa coincides with introduction of a drug product from Process C(█) or Process C(█), PK samples will be collected at the infusions at which patients receive their usual dose of olipudase alfa under the new process.

Blood samples for pediatric patients are drawn at different intervals than samples in adult patients ([Section 1.6](#), [Table 12](#) and [Table 11](#), respectively) and in different volumes ([Section 9.5](#)).

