9.3.8.3 Pharmacokinetic sampling and parameters in adults

9.3.8.3.1 Sampling time in adults

Pharmacokinetic sampling will occur at the time points listed in [Section 1.1](#) and [Section 1.6](#). Specific time points are detailed in [Table 11](#). If a patient receives only a partial infusion (eg, due to a safety concern), PK sampling will be repeated the next time the patient receives that dose. If a repeat is required, all PK time points will be repeated.

Windows around PK blood samples are ± 10 minutes for collection times less than 8 hours and ± 3 hours for collection times of 8 hours or longer post infusion.

Blood samples may be drawn for PK assessments using an indwelling catheter from an arm that is not used for dose administration. The exact time of dose administration (start and stop times of infusion), rate of infusion, and dose will be recorded along with exact sampling times.

If a manufacturing scale change occurs, serial blood samples for PK will be collected at all of the same time points with the last infusion of olipudase alfa produced at the original scale and with the first infusion of olipudase alfa produced at the new scale. For introduction of drug product from Process C(█), PK sample collection will only take place at the second infusion under Process C(█).

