9.5 SAMPLED BLOOD VOLUME

For all pediatric patients, no more than 7 mL/kg of blood will be collected during any 8-week period. Additional blood samples may be collected at the investigator's discretion for patient safety monitoring.

If a PK or IgG sample collection for the planned introduction of drug product from Process C(█) was erroneously taken, the future sample collection will be adjusted according to the blood volume allowed per each age cohort in order to avoid excessive blood withdrawal. For specific details, please refer to Study Manual.

[Table 17](#) shows the approximate sampled blood volume in patients ages 12 to <18 years old in the first 5 years.

Table 17 - Approximate sampled blood volume in patients ages 12 to <18 years in the first 5 years

Assessment	Volume (mL) per sample	Number of samples per year	Total (mL) per year
Liver function, clinical chemistry, and lipid profile	5.0	4	20.0
Hematology	2.0	4	8.0
Coagulation	3.6	4	14.4
Safety biomarkers	6.5	4	26.0
Efficacy biomarkers	10.0	4	40.0
Serum bone-specific AP and C-telopeptide	2.5	4	10.0
Metabolites in plasma and/or DBS	3.2	4	12.8
Anti-olipudase alfa IgG and neutralizing antibodies in IgG-positive patients	3.5	4	14.0
Olipudase alfa pharmacokinetics	1.5	7	10.5
		Approximate total per year	155.7
		Approximate total per 5 years	778.5

AP=alkaline phosphatase

Table 18, Table 19 show the additional approximate sampled blood volume in patients ages 12 to <18 years old with an olipudase alfa manufacturing scale change or manufacturing process update respectively. Not all of the patients will be exposed to both changes; therefore, blood volume would be calculated individually. To avoid excessive blood volume withdrawn, if similar assessment is regularly scheduled (IgG, PK or hematology and coagulation) in the same month, priority is given to manufacturing scale or updated manufacturing process update assessments and the regular similar assessments may be canceled.

Table 18 - Additional approximate sampled blood volume in patients ages 12 to <18 years with an olipudase alfa manufacturing scale change

Assessment	Volume (mL) per sample	Number of samples	Total (mL)
Anti-olipudase alfa IgG and neutralizing antibodies in IgG-positive patients	3.5	1 sample per month for 6 months	21.0
Olipudase alfa pharmacokinetics - prior to manufacturing scale change	1.5	7	10.5
Olipudase alfa pharmacokinetics - post manufacturing scale change	1.5	7	10.5
Approximate additional volume per study			42.0

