11.6.4 Analyses of pharmacokinetic and pharmacodynamic variables

Plasma concentration-time data will be analyzed using actual dosing and sampling times by noncompartmental methods. Pharmacokinetic parameters will be calculated for each patient and summarized by dose level and study week. As data permit, PK parameters may also be evaluated across dose level at each manufacturing scale or manufacturing process. Metabolite levels will be summarized by dose level and time point using descriptive statistics.

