#### **2.4.8.15 Subgroup analyses for efficacy (Patients from pediatric study DFI13803)**

For Patients from pediatric study DFI13803, below subgroup analyses will be performed.

To assess persistence of efficacy in patients with different baseline disease severity, the following subgroup analysis will be conducted:

- Spleen volume (MN) by baseline spleen volume severity (severe vs not severe). Severe patients is defined as baseline spleen volume  $>15$  multiple of normal (MN).
- % predicted DLco by baseline % predicted DLco severity (severe vs not severe). Severe patients is defined by baseline % predicted DLco  $<40\%$ .

To assess the impact of immunogenicity on efficacy, descriptive summaries for spleen volume and platelet count will be conducted for the following two groups of patients treated with olipudase alfa:

- Patients with treatment emergent anti-drug antibody (ADA) positive defined as either treatment induced or treatment boosted ADA positive at any time during olipudase alfa treatment.
- Patients with ADA negative defined as neither treatment induced or treatment boosted ADA positive at all time during olipudase alfa treatment.

For all the above subgroup analyses, within each subgroup, the change or percent change from baseline at each longitudinal time point will be summarized and analyzed with the analysis of covariance (ANCOVA) approach with baseline as covariate.

The efficacy measures (spleen volume and platelet count) will also be compared between manufacturing Process B, Process C (█) and Process C (█) as described below.

- To compare Process B and Process C (█), descriptive summaries for above efficacy measures will be created for the patients who started on Process C (█) only (patients never on Process B) versus patients who started on Process B and then switched to Process C (█) (Patients who were ever on Process B). In this analysis, the data when patients were exposed to Process C (█) will be excluded.
- Descriptive summaries for above efficacy measures will be created for the patients who did not switch to Process C (█) yet (patients never on Process C (█)) versus patients who switched to Process C (█) (Patients ever on Process C (█)).
- For patients who switched to Process C(█) and patients who switched to Process C (█) separately, the individual patient plot of observed values at each time point for above efficacy measures will be created with time point for start of each process (B, C (█) and C (█)) added on the plot.

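### PK is sampled in the same patient just before and just after the Process B-to-C change, but no within-patient comparison of the two profiles is specified

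*SAP*

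**What the plan says.** **Sampling, first change (B to C, the manufacturing scale change).** Protocol 9.3.8 states, for patients with no break in dosing: "PK sample collection will take place at the patient's last infusion under the current manufacturing scale and at the first infusion". The first infusion meant is the first on the new process. For adults, Protocol 9.3.8.3.1 adds that "serial blood samples for PK will be collected at all of the same time points with the last infusion of olipudase alfa". The same points then apply to the first infusion at the new scale. Tables 14 and 16 count a profile on each side of the change for adults and for every pediatric cohort. Appendix B (Amendment 01, item 12) gives the reason for this sampling as data on drug comparability.

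**Sampling, later process update.** Here "PK sample collection will only take place at the second infusion under" the updated process (Protocol 9.3.8.3.1). No matching old-process profile is scheduled.

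**Who switches.** Protocol 9.5: "Not all of the patients will be exposed to both changes". For efficacy, SAP 2.4.8.15 separates "patients never on Process B) versus patients who started on Process B and then switched to Process C", so some patients have no Process B data.

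**Analysis.** SAP 2.4.9.2: "Values will be reported for individual patient and summarized by age group cohorts, dose level, manufacturing process and study week as appropriate". The estimation method is "non-compartmental methods, or nonlinear mixed effects modeling, based upon patient age and data suitability". The same section's detailed list of descriptive statistics is by visit, dose level and age cohort, and does not mention process. Protocol 11.6.4 says only that "PK parameters may also be evaluated across dose level at each manufacturing scale or manufacturing process".

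**The concern.** Two infusions about two weeks apart in one patient at one dose are close to ideal for asking whether a process change moved exposure: each patient is their own control, and growth and time on treatment hardly differ. Pediatric patients give extra blood for it. Protocol 9.5 budgets 10.5 mL on each side of the change at ages 12 to <18, 9.0 mL at ages 3 to <12 and 7.5 mL in the youngest group.

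The planned output does not ask that question directly. A table by process can hold different patients in its two columns. A table by study week puts the two members of a pair in different rows. A reader given only such tables cannot recover the within-patient change or its uncertainty, so the comparability evidence that the sampling was meant to provide would be weaker than the data allow.

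**Working it through.** The plan gives no PK variance, within-patient correlation, number of switchers, precision target or comparability margin, so there is no stated figure to reproduce. The sample counts do confirm that both profiles are budgeted. With 5 yearly profiles, 2 at the scale change and 1 at the update, that is 8 profiles: adults 8 × 8 = 64, adolescents 7 × 8 = 56, children 6 × 8 = 48, infants 5 × 8 = 40. All agree with Tables 14 and 16.

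**1. Can the estimate shift?** If the same patients fill both columns, the ratio of geometric means equals the paired estimate. Suppose instead that a fraction f of the Process C column was never on B, and that these patients differ from the switchers by δ in mean log AUC on Process C. The apparent log ratio then moves by f × δ whatever the process does. The documents give neither f nor δ.

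**2. Do the columns give the right uncertainty?** Combining two column SEMs gives √(SEM_B² + SEM_C²). For paired data the variance of the difference also contains −2 × covariance, which column summaries do not show.

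**3. How much could pairing gain?** Assumptions, none from the documents: log AUC, within-patient SD sw = 0.15-0.25, between-patient SD sb = 0.30-0.40, n = 12 pairs, 90% CI.

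- Paired half-width = t(0.95, n−1) × √2 × sw / √n, with t(0.95, 11) = 1.796
- Unpaired half-width = t(0.95, 2n−2) × √(2(sw² + sb²)/n), with t(0.95, 22) = 1.717
- Implied correlation ρ = sb² / (sb² + sw²)

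| sw | sb | ρ | Paired CI (×/÷) | Unpaired CI (×/÷) | Log-width ratio |
|---|---|---|---|---|---|
| 0.15 | 0.30 | 0.80 | 1.116 | 1.265 | 2.14 |
| 0.15 | 0.40 | 0.88 | 1.116 | 1.349 | 2.72 |
| 0.20 | 0.35 | 0.75 | 1.158 | 1.327 | 1.93 |
| 0.25 | 0.30 | 0.59 | 1.201 | 1.315 | 1.49 |
| 0.25 | 0.40 | 0.72 | 1.201 | 1.392 | 1.80 |

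Example for the fourth row: paired 1.796 × 1.4142 × 0.25 / 3.4641 = 0.183; unpaired 1.717 × √(2 × 0.1525 / 12) = 0.274; 0.274 / 0.183 = 1.49. Crossing the full assumed ranges gives 1.49 to 2.72.

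**4. When is there no gain?** Unpaired width over paired width = [t(2n−2) / t(n−1)] / √(1−ρ). With n = 5 and a 90% CI, t(8) / t(4) = 1.860 / 2.132 = 0.872, so pairing is no narrower unless ρ exceeds 1 − 0.872² = 0.24 (0.31 for a 95% CI). With n = 12, a 90% CI and ρ = 0.5, the ratio is only 1.35.

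**The case against.** A reader might infer that the paired data go unused. They do not: SAP 2.4.9.2 reports individual values and allows nonlinear mixed-effects modelling, which keeps the within-patient structure. What is absent is a stated paired contrast or a process term.

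A reader might also infer that the plan throws away about half its precision. The documents do not support a figure. The SAP's PK analysis by process is descriptive, so no planned between-process interval is widened. The unpaired interval above is a yardstick for this review, and its width rests on assumed SDs and an assumed number of pairs. Even the upper limit on pairs is unclear, since the SAP gives the study size as about 25 in section 1.1 and as 17 in section 1.3.

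Three limits on the remedy also stand:

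- Pediatric sampling is deliberately sparse (Protocol 9.3.8.4.1). In Table 12 the child and infant cohorts have no end-of-infusion sample. Protocol 9.3.8.4.3 therefore allows model-based analysis, with non-compartmental parameters only where appropriate.
- Confidence intervals by age cohort would rest on very few pairs. At 4 pairs the formula above gives ×/÷ 1.28 to 1.52.
- The later update has no adjacent old-process profile. Routine PK is yearly and only in the first 5 years, so the nearest earlier profile could be a year or more old in a growing child. Pairing with it brings time confounding back.

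PK is a secondary objective in an extension that was not powered. That argues against a formal test, but not against estimating the quantity the samples were drawn to provide.

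**Conclusion.** The point holds for one of the two process changes, for patients who switch, and when treatment is not interrupted. Within those limits the sampling is paired and meant to inform comparability, yet neither the SAP nor the protocol specifies a within-patient comparison. Summaries by process can mix switchers with patients never on Process B, and their column SEMs do not describe the uncertainty of the within-patient change.

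The size is conditional. Under the assumed SDs and 12 pairs, an unpaired 90% interval would be about 1.5 to 2.7 times wider on the log scale; with about 5 pairs and low correlation, pairing may gain nothing. The case for the change does not depend on that range: the within-patient ratio answers the intended question, is not affected by which patients enter each column, and needs no new data.

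**What to change.** Add to SAP 2.4.9.2:

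- **B-to-C change.** For patients sampled on both sides at the same mg/kg dose, report the new/old ratio of AUC and Cmax as one overall geometric mean ratio with 90% CI, the number of pairs, and a paired plot. By age cohort, show individual ratios only, without a CI.
- **Sparse pediatric profiles.** Where sampling does not support non-compartmental AUC, use model-based individual estimates or a process effect in the mixed-effects model.
- **Later process update.** Show the second-infusion values beside the patient's latest earlier profile at the same dose, descriptively, with the time gap stated and no comparability claim.

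Cost: one extra table and one figure from data already collected, with no added sampling.

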## **2.4.10 Analyses of health outcome questionnaires and cognitive and adaptive function**

Patients from adult study DFI13412 fill out different questionnaires from the patients from the pediatric study DFI13803, hence these will be analyzed separately.

#### **2.4.10.1 For patients from adult study DFI13412**

##### ***Brief Fatigue Scale (BFI)***

The severity and interference of fatigue as measured by BFI (individual questions as well as scale score) will be summarized separately, along with change from baseline, at each scheduled time point.

##### ***Brief Pain Scale (BPI) - SF***

The severity and interference of pain as measured by BPI-SF (individual questions as well as scale score) will be summarized separately, along with change from baseline, at each scheduled time point.

##### ***Chronic Respiratory Disease Questionnaire (CRQ-SAS)***

The 4 dimensions of CRQ-SAS - dyspnea, fatigue, emotional function, and the patient's feeling of control over the disease (mastery) - will be summarized separately, along with change from baseline, at each scheduled time point.

##### ***SF-36***

The 8 scales measured by SF-36 - physical functioning, role physical, bodily pain, mental health, role emotional, social functioning, vitality, and general health - as well as the 2 summary measures of physical health (PCS) and mental health (MCS) will be summarized separately, along with change from baseline, at each scheduled time point.

##### ***Niemann-Pick B Health Assessment Questionnaire (NPB-HAQ)***

Three domains of NPB-HAQ - resource utilization, symptoms and physical activity – will be summarized separately with each question at each scheduled time point.

- For resource utilization in the past year of each scheduled time point, the following measures will be summarized: the total nights spent in the hospital, the number of emergency room or urgent care visits.
- For symptom in the past month of each scheduled time point, frequency and level of bothersome of each symptom will be listed.
- For physical activity in each scheduled time point, the number and percentage of patients at each frequency of physical activities will be summarized.

#### **2.4.10.2 For patients from pediatric study DFI13803**

The patient transitioning from the pediatric study will use the age-appropriate questionnaires at the entry to the extension study. As the study progresses if the patients crosses the threshold of the questionnaire, the new age appropriate questionnaire will be used, until the maximal age range (young adult). Since the baseline of the original study may use a different questionnaire than what

is used in the extension study, the change from baseline summaries will not be produced; however, when the same questionnaire is used for baseline and post-baseline visit, summary of change from baseline will be provided.

### ***PedsQL Generic Core Scales***

Individual scale scores, Psychosocial Health Summary Score, Physical Health Summary Score and the Total Scale Score will be calculated based on the 0-100 scale scores. Their computed values will be summarized at each scheduled time point.

### ***PedsQL Multidimensional Fatigue Scale***

Individual scale scores and the Total Scale Score will be calculated based on the 0-100 scale scores. Their computed values will be summarized at each scheduled time point.

### ***PedsQL Pediatric Pain Questionnaire***

Only the first two items out of 3 items are scored based on the 100 mm VAS. The observed values will be summarized at each scheduled time point.

### ***Developmental Profile (DP-3) and Adaptive Behavior Assessment System (ABAS-3)***

A listing of DP-3 and ABAS-3 raw and generated scores will be provided.

For the DP-3, by-patient bar graphs will be generated to demonstrate subject's performance over time using percentile rank and standard score for each content area (Physical, Adaptive Behavior, Social-Emotional, Cognitive, Communication) and General Development Score at all scheduled visits.

For the ABAS-3, by-patient bar graphs will be generated to demonstrate subject's performance over time using percentile rank and standard scores for the General Adaptive Composite and three adaptive domains (Conceptual, Social, and Practical) at all scheduled visits.

In addition, to illustrate patient's performance on the DP-3 and ABAS-3 collectively, group graphs by patient age will be developed showing tool standard scores of patients over time. One graph for the ABAS-3 General Adaptive Composite Standard Score and one graph for the DP-3 General Development Score Standard Score.

## **2.5 PATIENT NARRATIVES**

Patient narratives criteria for this study are as follows:

- Deaths
- Serious adverse event
- Adverse Events leading to permanent treatment discontinuation

- Adverse events of special interest including the followings:
  - Protocol defined IARs (as specified in [Section 2.1.3.1](#))
  - Pregnancy of female patient or partner of a male patient
  - Symptomatic overdose of study drug
  - Any increase in AST, ALT, total bilirubin, or AP  $>3x$  baseline (prior to olipudase alfa therapy) and  $>$  ULN
  - Any increase in total bilirubin or AP  $>1.5x$  baseline in the presence of AST or ALT  $>2x$  ULN
  - Any increase in ALT or AST  $>3x$  the ULN combined with an increase in ALT or AST  $>2x$  baseline (prior to olipudase alfa therapy) with symptoms of fatigue, nausea, vomiting, right upper quadrant pain or tenderness (for adults only), fever, rash, or eosinophilia ( $>$  ULN)
  - Patients from pediatric study DFI13803: asymptomatic overdose of study drug

Patients who meet these criteria will be listed and provided to the medical writer.

